14.6 SUSAR reporting

Cardiff University is undertaking the duties of trial Sponsor and has delegated to the CTR the responsibility for reporting SUSARs and other SARs to the regulatory authorities (NCAs and relevant ethics committees) and to AstraZeneca as follows:

SUSARs which are fatal or life-threatening must be reported to the MHRA and REC within 7 calendar days of receipt at the CTR.

SUSARs that are not fatal or life-threatening must be reported to the MHRA and REC within 15 days of receipt at the CTR.

If report is incomplete then additional follow-up information should be reported within a further 8 calendar days of submitting the initial report, for all fatal and non-fatal, life-threatening and non-life-threatening SUSARs.

Any additional, relevant information must be reported within a further 15 days.

14.7 Safety Reports

A list of all SAEs and SARs (expected and unexpected) will be reported annually to the MHRA, REC, trial sponsor and AstraZeneca in the form of a Development Safety Update Report (DSUR). This report must be submitted within 60 days of the anniversary of the MHRA Clinical Trial Authorisation (CTA) approval date.

The CTR will report a list of all SAEs and SARs (expected and unexpected) and any other safety recommendations to all PIs annually throughout the course of the trial. This frequency may be reviewed and amended as necessary. This reporting will be done via the Investigator safety report (ISR).

14.8 Contraception and pregnancy

14.8.1 Definitions

Women of Non-Childbearing Potential

Women of non-childbearing potential are defined as female participants who are permanently surgically sterilized or postmenopausal. Permanent sterilization includes hysterectomy and/or bilateral oophorectomy and/or bilateral salpingectomy at least 6 weeks before screening. Bilateral oophorectomy alone is acceptable only when the reproductive status of the woman has been confirmed by follow-up hormone level assessment.

For women aged < 50 years, postmenopausal is defined as having both a history of \geq 12 months amenorrhea prior to randomization, without an alternative cause, following cessation of exogenous sex-hormonal treatment, and an FSH level in the postmenopausal range. Until FSH is documented to be within menopausal range, the participant is to be considered of childbearing potential.

For women aged \geq 50 years, postmenopausal is defined as having a history of \geq 12 months amenorrhea prior to randomization, without an alternative cause, following cessation of exogenous sex-hormonal treatment.

Women of Childbearing Potential (WOCBP)

A woman is considered of childbearing potential, i.e. fertile, following menarche and until becoming postmenopausal unless permanently sterile.

Pregnancy Testing Women of childbearing potential can be included only after a negative urine pregnancy test. Urine pregnancy testing will be done as per the SoA (see Section 13). If urine tests positive or indeterminate, a quantitative serum β -hCG will be performed for confirmation.

14.8.2 Contraception

Women of Childbearing potential

AZD7442 in this trial has a demonstrated or suspected human teratogenicity/fetotoxicity. Women of childbearing potential who are sexually active must agree to use, with their non-sterilized male partner, an approved method of highly effective contraception from the time of AZD7442 administration until 3 months after. In instances where a WOCBP has a sterilized male partner, the vasectomized partner must have received a medical assessment of surgical success. Women should be stable on their chosen method of birth control for at least one month before dosing. Highly effective contraception is summarized in Table 11.

Table 11: Highly effective methods of contraception

Barrier method	Hormonal method	
 Intrauterine device Intrauterine hormone-releasing system (IUS)^a Bilateral tubal occlusion Vasectomized partner ^b Sexual abstinence ^c 	 Combined (oestrogen- and progestogen-containing hormonal contraception) associated with inhibition of ovulation Oral (combined pill) Intravaginal Injectable Transdermal (patch) Progestogen-only hormonal contraception associated with inhibition of ovulation Oral Injectable Transdermal (patch) 	

a This is also considered a hormonal method.

b Provided that partner is the sole sexual partner of the woman of childbearing potential study participant

and that the vasectomized partner has received medical assessment of the surgical success.

c Sexual abstinence is considered a highly effective method only if defined as refraining from heterosexual

intercourse during the entire period from the time of AZD7442 administration until 3 months after and if it is

the preferred and usual lifestyle of the participant.

Male Participants

To avoid transfer of fluids to a sexual partner, all male participants must use a condom starting from the time of AZD7442 administration until 3 months after. Contraception for female partners of childbearing potential may be considered, but is not required for this protocol.

Participants will be instructed that if their partner becomes pregnant in the three months following AZD7442 administration, this should be reported to the PI. The PI should also be notified of pregnancy occurring within 3 months of AZD7442 administration but confirmed after completion of the trial. In the event that a participant's partner is subsequently found to be pregnant within 3 months of the participant receiving AZD7442, then consent will be sought from the partner and, if granted, any pregnancy will be followed, and the status of mother and/or child will be reported to the Sponsor after delivery. A pregnancy notification form and follow-up will be completed.

14.8.3 Donation

Ova Donation

Female participants should not donate ova for at least 3 months after the AZD7442 dose.

Sperm Donation

Male participants should not donate sperm for at least 3 months after the dose of AZD7442.

14.8.4 Pregnancy reporting whilst participating in the trial

Pregnancy, or the pregnancy of a partner occurring whilst participating in the trial, is not considered an SAE, however, a congenital anomaly or birth defect is. Other cases (e.g. termination of pregnancy without information on congenital malformation, and reports of pregnancy exposure without outcome data) should not normally be reported as such. When pregnancy occurs in a trial, either in a female participant or the female partner of a male participant, this should be followed up until at least the end of pregnancy, whether that is a live birth, abortion etc. Without follow-up of the pregnancy, it would not be possible for the CTR to know if a congenital anomaly or birth defect occurred, and therefore if there was an SAE that must be included in the safety evaluation of the IMP. Information on a pregnancy in a trial participant will be captured on the CTR Pregnancy Report Form supplied to sites by the CTR.

Pregnancy occurring within 3 months of AZD7442 administration and reported during the trial will be followed up for safety from the post-dose administration to end of the trial, or until term, to identify pregnancy outcome, whichever is later.

Female participants who become pregnant after dosing will continue to have all PK samples collected. These do not represent a safety risk. Any complications during the planned follow-up of any pregnant

RAPID-PROTECTION Protocol v.5.0 09/05/2023

participant (if any) will be discussed between the PI and AstraZeneca, and a decision to halt or continue any further sampling will be made on a case-by-case basis.

15 Statistical considerations

15.1 Randomisation

Participants will initially be enrolled and registered for the trial and all will receive the trial treatment AZD7442. At 28 days of follow up participants will subsequently be randomised in a 1:1 ratio to one of the two booster vaccines (Spikevax bivalent (Original/Omicron) and Comirnaty bivalent (Original/Omicron BA.1)). A computer-based randomisation allocation process will use random permuted blocks of varying sizes. The trial statistician will produce the randomisation schedule prior to enrolling participants.

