	To identify markers that predict loss/maintenance of AZD7422 titres, response to SARS-CoV-2 vaccines, SARS- CoV-2 infection and adverse events across the cohort.	Immune, clinical and laboratory parameters will be assessed as predictive biomarkers for the primary and secondary trial endpoints.

6 Trial design and setting

The trial is a multicentre, open-label, phase II trial with a randomised comparison of vaccine booster type at 28 days following AZD7442 treatment. Up to 350 patients will be recruited and treated at NHS sites including those already participating in the studies of candidate SARS-CoV-2 vaccines and other interested sites in the UK. Participants will be recruited from groups known to be highly vulnerable to SARS-CoV-2 and therefore likely to benefit from AZD7442 as defined by those recommended as high priority by the Joint Committee on Vaccination and Immunisation (JCVI) (see appendix 1). Patients will be stratified by cohort into 4 groups: Haematological malignancies, Solid tumours, Renal and Hepatic disorders and inflammatory disorders.

All participants will receive AZD7442 treatment followed by vaccination with SARS-CoV2 vaccine booster 28 days later. Immunogenic response will be measured at baseline, throughout treatment and at follow up. The design of the prospective cohort will be initially observational with all participants receiving AZD7442 treatment followed by randomisation to a vaccination with SARS-CoV-2 vaccine booster. The cohorts will be sub divided into subgroups for comparison to healthy volunteers.

Participants will be subdivided into 4 subgroups (see figure 2); up to 120 of these patients enrolled at Oxford University Hospitals NHS site will have additional translational bloods for the additional immunological studies described within the protocol. The Oxford site will decide in conjunction with

the trial management team on which patients from each cohort at the Oxford site will have standard study bloods or translational bloods tests.

Where subjects have conditions that allow entry into more than one cohort of the study then the subject will be allocated into the cohort for the condition that they have had the longest, should that cohort be full, then the subject will be allowed to enter the other cohort for their other condition.

Cohort 1: Haematological malignancies (anticipated 70 participants)

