9.5 Registration and randomisation

Once participants are identified, consented and deemed eligible, they will be assigned a unique trial ID and randomised by the treating team via the same portal. Participants will be randomised to receive one of two boosters in a 1:1 ratio:

Arm 1: Comirnaty bivalent (Original/Omicron BA.1)

Arm 2: Spikevax bivalent (Original/Omicron)

The trial will be unblinded and therefore both the participant and the site research team will know the treatment allocation. The trial pharmacist, research nurse and laboratory team will be notified of the randomisation allocation and trial ID number. A copy of the Randomisation Confirmation, signed Informed Consent Form, and Eligibility Checklist should be filed within the Investigator Site File.

Registration and Randomisation

Patient enrolment for this trial will be through the use of a web-based system: https://trials.cardiff.ac.uk/portal

Details of how to access the system will be supplied to Investigators as part of the trial set-up.

If any problem with the web-based system or it is unavailable, please email the trial team:

[contact]

10 Withdrawal & lost to follow-up

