13.1 Assessments

Baseline Assessments

All baseline assessments should be performed after consent has been obtained and within 28 days of treatment. Participants will be required to attend clinic for blood sample collection and treatment. The following assessments will need to be done:

- Completion of eligibility checklist form
- Participant informed consent
- Full Medical History
- Randomisation as per Section 9.5 of the protocol
- Participants should be asked about their previous SARS-CoV-2 vaccination history. The information should be collected on the SARS-CoV-2 vaccine form.
- Prior and Concomitant Medications Review of any medications received within 28 days before the first dose of trial treatment
- Participant behavioural questionnaires (risk behaviour changes, PROMIS 10, EQ-5D-5L)

AZD7442 treatment (this can be done on the same day as baseline assessments)

Day 0

- A negative urine dipstick pregnancy test should be performed to confirm eligibility for women of child-bearing potential.
- Toxicity assessment (CTCAE 5.0)
- Blood sample collection and completion of the sample eCRF
- Safety bloods (full blood count (FBC), Urea and electrolytes (U&E), Liver function test (LFT) and bone profile)
- Full Physical Examination including vital signs, weight and height
- Blood sample collection prior to AZD7442 dosing and completion of the sample eCRF
- Routine (asymptomatic) lateral flow testing for SARS-CoV-2 infection (only subset of participants). If the lateral flow test is positive for SARS-CoV-2 infection, a nasal PCR swab should be taken to be sent for testing.

NB: The assessments above should be performed *before* the administration of AZD7442.

• Dosing with AZD7442

On Day 14 post AZD7442 (+/- 3 days):

• Toxicity assessment via telephone consultation with patient to check on symptoms.

On Day 28 post AZD7442 (+/- 3 days):

- Clinical review
- Vital signs
- Blood sample collection and completion of the sample eCRF
- Safety blood samples (FBC, U&E, LFT and bone profile)
- Concomitant Medications Review
- Toxicity assessment (CTCAE 5.0)
- Routine (asymptomatic) lateral flow testing for SARS-CoV-2 infection (only subset of participants). If the lateral flow test is positive for SARS-CoV-2 infection, a nasal PCR swab should be taken to be sent for testing.

NB: The assessments above should be performed *before* the administration of SARS-CoV-2 vaccine booster.

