15.7 Inclusion in analysis

All enrolled participants will be included in analyses.

16 Analysis

A detailed Statistical Analysis Plan will be produced prior to the database lock. In general, a treatment policy approach to estimands will be used to deal with intercurrent events.

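### Sections 9.5 and 13.1 randomise to the booster at baseline and section 15.1 at Day 28, so the population for the Day 56 vaccine comparison is undefined

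*Protocol*

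**What the plan says.** The protocol places the booster randomisation at two different times.

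**At entry.** Section 9.5 says that as soon as consent and eligibility are settled, "they will be assigned a unique trial ID and randomised by the treating team via the same portal". The baseline list in section 13.1 includes "Randomisation as per Section 9.5 of the protocol", and the same section says "All baseline assessments should be performed after consent has been obtained and within 28 days of treatment". The Day 28 list in section 13.1 contains no randomisation step; it only gives the booster according to an allocation that already exists.

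**At Day 28.** Section 15.1 registers participants, gives all of them AZD7442, and then states "At 28 days of follow up participants will subsequently be randomised in a 1:1 ratio to one of the two booster vaccines". Section 6 has the same order, "with all participants receiving AZD7442 treatment followed by randomisation to a vaccination with SARS-CoV-2 vaccine booster".

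Table 6, the schedule of assessments, has no row for randomisation. Sections 9.5 and 15.2 make the trial open label, with participant and site team aware of the allocation. Section 15.7 defines the analysis population in one sentence: "All enrolled participants will be included in analyses". Section 16.1.2 compares the vaccines by ANCOVA, with the outcome at Day 56.

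**The concern.** Vaccine against vaccine is the only contrast in this trial that randomisation protects. Who belongs to it depends on when allocation happens.

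If allocation is at baseline, participants and staff know the booster brand for weeks before it is given. Anyone who leaves in that interval is a randomised participant without a booster, and the decision to leave can depend on the brand. If allocation is at Day 28, the same person was never randomised and has no arm. The two rules give different denominators and different exposure to selective loss, and the protocol does not say which one governs.

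A statistical analysis plan cannot repair this, because the time of allocation is a conduct rule that sites carry out.

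**Working it through.** **Interval between allocation and booster, if allocated at baseline.** The booster is due at Day 28 ± 3 (section 13.1), which is Day 25 to Day 31. Baseline is between 0 and 28 days before AZD7442.
- Shortest: 25 days (baseline on Day 0).
- Longest: 28 + 31 = 59 days.

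**The plan's own figure.** Section 15.3 needs 4 × 70 = 280 and allows 20% loss: 280 / (1 − 0.20) = 350, which reproduces. Planned loss is 350 × 0.20 = 70.

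**When the 70 losses fall.** Section 15.3 gives no timing. Section 10.2 counts loss up to the end of follow-up, which is Day 180. Under baseline allocation all 70 follow randomisation. How many precede the booster has to be assumed. Suppose the 20% accrues at a constant hazard over T days from dosing, so that loss by Day 28 = 350 × (1 − 0.8^(28/T)):

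| T (days) | Share lost by Day 28 | Lost by Day 28 | Lost later | Left to randomise at Day 28 |
|---|---|---|---|---|
| 180 | 3.4% | 12 | 58 | 338 |
| 112 | 5.4% | 19 | 51 | 331 |
| 56 | 10.6% | 37 | 33 | 313 |
| 28 | 20.0% | 70 | 0 | 280 |

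The last two columns follow by subtraction from 70 and from 350.

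**Effect on the analysis population.** Under section 15.1, the 12 to 70 people lost by Day 28 are enrolled but have no arm, so the all-enrolled rule cannot be applied to the vaccine comparison. Under sections 9.5 and 13.1 they have an arm and the rule can be applied, but they have no booster.

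**Illustrative bias under baseline allocation.** Neither input below comes from the protocol. Assume that those who leave would have responded 1 SD lower than those who stay, and that loss splits 15:25 between the arms. If overall pre-booster loss is p, the arms lose 0.75p and 1.25p. The bias among those who stay is (1.25p − 0.75p) × 1 SD = 0.5p SD.
- p = 3.4%: 0.017 SD
- p = 10.6%: 0.053 SD
- p = 20%: 0.10 SD (15% against 25%)

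The standard error of the difference with 140 per arm is √(2/140) = 0.12 SD. With 169 per arm (338 / 2) it is √(2/169) = 0.11 SD. Neither allows for baseline adjustment or for loss between Day 28 and Day 56.

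**Text that depends on randomisation being at entry.** Four other places use randomisation as the entry point: the instruction on eligibility queries in section 8, exclusion 14 (blood drawn in the preceding 30 days), the eligibility checklist in section 9.1, and the postmenopausal definition in section 14.8.1. Read with section 15.1, these would be judged about four weeks after AZD7442 was given, which makes no sense for entry criteria.

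**The case against.** The strongest reply is that the operational text is coherent and section 15.1 is the outlying sentence. Sections 9.5, 13.1, 9.1 and 8 and exclusion 14 all fit entry randomisation through one web portal, so practice may well be uniform. That is plausible, and nothing in the protocol shows that sites differ. But section 6 sides with section 15.1, and the document does not say which governs.

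It can also be said that section 16 adopts a treatment-policy approach, under which randomised but unboosted participants are retained. That holds for baseline allocation. It does not help under Day 28 allocation, where early leavers have no arm. Nor does Day 28 allocation remove every loss: loss between Day 28 and Day 56 follows an open allocation under either timing.

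Three stronger readings are tempting, and the documents do not support them.
- *That all of the 20% loss precedes the booster.* A reader might infer this from the 280 completed Day 28 datasets in section 15.3. That figure triggers an analysis and does not time the loss, and section 10.2 counts loss to the end of follow-up. Seventy is the upper bound.
- *That section 15.1 contradicts a promise of stratified randomisation.* Section 6 says "Patients will be stratified by cohort into 4 groups", and section 15.3 uses similar language for recruitment. Both can describe cohort structure. Section 15.1 is silent on strata and does not exclude them.
- *That knowledge of the arm distorts the translational-blood subset.* Section 6 has the Oxford site decide together with "the trial management team on which patients from each cohort at the Oxford site will have standard study bloods or translational bloods tests". Nothing says that the choice follows allocation, and a random draw would be a preference, not a correction.

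**Conclusion.** Wrong as written, and it should be fixed. The protocol gives two incompatible times for the same randomisation, and the all-enrolled rule cannot define the vaccine comparison under one of them.

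The certain part is the contradiction, together with the fact that baseline allocation puts all 70 planned losses after randomisation, with the brand known for 25 to 59 days before the booster. The number lost before the booster, 12 to 70 of 350, rests on an assumed accrual pattern. The bias of roughly 0.02 to 0.10 SD rests on a further assumed imbalance and an assumed 1 SD difference. It shows scale and does not predict a result. Even its upper end is below one standard error.

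The reach is limited. Vaccine against vaccine is a secondary objective. The target of 350 and the Day 28 comparison with external controls, on which the sample size rests, do not depend on when participants are randomised.

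**What to change.** 1. Make sections 9.5, 13.1 and 15.1 state one randomisation time, and add a randomisation row to Table 6.
2. For participants already enrolled, take the recorded randomisation date as fact. Define the set for the booster comparison as all randomised participants, add cohort as a covariate to the ANCOVA, and report loss between allocation and booster by arm. Keep the all-enrolled rule for the analyses that do not need an arm.
3. If recruitment resumes, randomise at the Day 28 visit just before the booster, so that earlier loss falls outside the randomised comparison. Re-anchor the entry text in section 8, exclusion 14, section 9.1 and section 14.8.1 to registration in the same amendment; otherwise the eligibility windows would move past dosing.

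The cost is wording, a portal setting if step 3 applies, and one covariate that is already recorded. A small downside of step 3 is that both vaccines must be in stock on the day. Recruitment was paused in April 2023 (section 13.1.1), before this protocol version, so step 3 matters only if it restarts. Steps 1 and 2 remain useful up to database lock.

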15.2 Blinding

This is an open label trial.

15.3 Sample size

We aim to recruit a total of 350 patients with immunosuppressive conditions. Sample sizes required for analysis of the various groups and outcomes have been based on SARS-COVID-2 IgG responses taken from the analysis of the PROVENT trial and other similar trials.

To compare Groups 1 + 2 + 3 + 4 with healthy volunteers from the PROVENT trial to show a reduction in IgG levels at 90% power with a 5% significance of 0.5 (log domain) and SD of 1 we need 70 patients. We expect this consideration to show that the variance in IgG levels is larger than healthy volunteers and have therefore powered to allow for the same comparison in each of the four sub-groups (1, 2, 3, 4) – 70 per group to give a total of 280 required. Allowing for loss to follow-up of 20% we will aim to recruit 350 patients stratified across the selected groups. To maximise heterogeneity at the group level and improve branching decisions, we will target even recruitment numbers in the subgroups of each group (level 3 in figure 2).

Analysis of the identified groups 1 + 2 + 3 + 4 will be undertaken once 280 completed datasets at 28 days have been achieved. If the variance in IgG levels is shown to be significantly different to healthy controls or more variable, then the analysis will progress to groups 1, 2, 3, and 4 individually and recruitment targets re-estimated.

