Patients with haematological malignancies and haemopoietic stem cell transplantation will be subdivided into patients receiving active therapy with immunosuppressive or immunomodulating agents (Cohort 1a) and patients receiving aggressive therapy expected to cause temporary ablation of immune function (Cohort 1b).

Cohort 2: Solid tumours (anticipated 70 participants)

The cancer cohorts will be subdivided into the following subgroups for comparison to healthy volunteers:

- Early cancer on systemic treatment (Cohort 2a)
- Advanced cancer on systemic treatment (Cohort 2b)

Cohort 3: Renal and Hepatic disorders (anticipated 70 participants)

Patients with renal (Cohort 3a) and hepatic disorders (Cohort 3b) will be divided into those receiving immunosuppression as part of their treatment, patients with advanced disease for example kidney disease on dialysis, or liver cirrhosis and liver and renal transplantation.

Cohort 4: inflammatory disorders (anticipated 70 participants)

Patients' inflammatory disorders will be divided into those receiving rituximab or not and those receiving other forms of immunosuppressants. Cohort 4a will include participants receiving rituximab and cohort 4b will include participants receiving non-rituximab immunosuppressants.

Each treatment group will then be compared to age-matched healthy volunteers from the mid-2021 phase 1 and 3 trials of AZD7442 and SARS-CoV-2 vaccine booster for both point estimator and variance, and across all patient cohorts.

This will be an adaptive trial that will extend recruitment in any sub-group where more information is required in order to come to a reliable estimator. The immunological assessments will be analysed to allow cohorts to be expanded in case of poor immunogenicity to SARS-CoV-2 or closed if good immunogenicity against SARS-CoV-2 is seen. Recruitment of patients from each group will be limited to ensure the trial captures a representative group of patients from all major immunosuppressive groups most at risk of SARS-CoV-2 mortality. The group sizes will be calculated based on the expected heterogeneity of the group and the degree of variability in the general population.

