16.1 Main analysis

16.1.1 Immunogenicity at 28 days following administration of AZD7442

The function and magnitude of SARS-CoV-2 specific antibody and T cell responses will be measured at baseline and at additional multiple timepoints after the administration of AZD7442. The immunological effect of the study interventions will be determined by comparison of the results of immunological assessments at baseline and subsequent time points.

Assays will quantify the amount of serum antibodies to the spike (S) and the nucleocapsid (N) antigens of SARS-CoV-2. This assay will enable the discrimination of antibody responses to SARS-CoV-2 that results from vaccination and/or SARS-CoV-2 infection. Ab function, including viral neutralisation will be assessed.

The magnitude and function of SARS-CoV-2 specific T cell responses following the booster vaccination will use assays that give insight into T cell function. Laboratories will measure neutralizing antibodies to SARS-CoV-2 using validated wild-type neutralization assay or pseudo-neutralization assays.

Comparisons of immunogenicity outcomes will be made with age and gender matched healthy controls from the PROVENT III trial. Group data will be requested from the PROVENT trial. Values will be log-transformed and mean and standard deviation calculated for the same groups at each timepoint. The PROVENT data will be used to calculate the overall standard deviation of a population with the same age / sex distribution as each of our cohorts at each timepoint. The mean and standard

deviation and its 95% confidence interval will be calculated for each cohort for comparison with the PROVENT data at each timepoint.

The ratio of the variances in the log transformed domain will be tested to assess if it is significantly different from 1. All tests will be one sided and focussed on if the trial patients perform less well than the healthy volunteers in terms of response to vaccine. Results will be reported as the ratio of variances, 95% confidence intervals and p values.

16.1.2 Immunogenicity at 28 days following administration of AZD7442 followed by a SARS-CoV-2 vaccine 28 days later (outcome measured at day 56)

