To assess if treatment with AZD7442 followed by a SARS-CoV-2 vaccine 28 days later will increase levels of anti-SARS-COVID-2-anti S-RBD neutralising antibodies in patients. This will be assessed in a hierarchical way firstly comparing age-matched healthy controls from the PROVENT III trial of the AZD7442 and AZD1222 all patients (groups 1, 2, 3 and 4) on both point estimator and variance and if the variance is greater than subdividing into the individual groups by patient group.

Comparisons will be made between each of the vaccines using an ANCOVA model with baseline value as a covariate. An exploratory analysis will be conducted to examine differences between the vaccine types and patient cohorts (see section 16.3 below).

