16.2 Sub-group & interim analysis

There are no planned sub-group analyses other than those described in the main analysis for the trial adaption process. Interim analyses are planned every 120 days and will consist of safety data reporting as described in the main analysis section.

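### Sections 15.3 and 16.1.2 open the cohort comparisons through a pooled variance check, although the cohorts were sized for a mean difference and Sections 6 and 16.1.1 set no such condition; the look at 280 completers leaves almost no room to adapt within 350

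*Protocol*

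**What the plan says.** Section 15.3 plans a comparison of IgG with healthy volunteers from the PROVENT trial: "at 90% power with a 5% significance of 0.5 (log domain) and SD of 1 we need 70 patients". It carries the same size to each of the four cohorts, "70 per group to give a total of 280 required", and inflates this for 20% loss to 350. Section 16.1.1 adds: "All tests will be one sided and focussed on if the trial patients perform less well than the healthy volunteers".

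The pooled analysis of all four cohorts "will be undertaken once 280 completed datasets at 28 days have been achieved". What follows depends on variance: "If the variance in IgG levels is shown to be significantly different to healthy controls or more variable, then the analysis will progress to groups" (meaning each of the four cohorts separately), with recruitment targets re-estimated. Section 16.1.2 applies the same hierarchy at day 56: the pooled patients are compared first, and "if the variance is greater than subdividing into the individual groups by patient group". Section 4.7 has a similar sentence.

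Other sections carry no such condition. Section 6 has each treatment group compared with age-matched healthy volunteers on both point estimate and variance. Section 16.1.1 has the mean and standard deviation, with a confidence interval, calculated for every cohort for comparison with PROVENT at each time point.

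On adaptation, Section 6 says the immunological results will be used "to allow cohorts to be expanded in case of poor immunogenicity to SARS-CoV-2 or closed if good immunogenicity against SARS-CoV-2 is seen", and the same section caps recruitment at 350. Section 16.2 states: "Interim analyses are planned every 120 days and will consist of safety data reporting". Section 13.1.1 records that recruitment was paused at the beginning of April 2023.

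**The concern.** The sample size answers a question about means: is IgG in a given cohort lower than in healthy volunteers by 0.5 log? The step that leads to the cohort tests asks a different question, whether the spread of the pooled patients exceeds that of controls. A mean deficit confined to one cohort adds little to pooled variance, so the condition can fail when the deficit the cohorts were sized for is present. The 90% power per cohort then holds only for trials in which the condition happens to be met.

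The protocol also gives two answers on whether the cohort comparisons are conditional. And the look meant to drive expansion or closure of cohorts is set at 280 completers, which is the whole planned evaluable sample.

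**Working it through.** **1. The plan's own figures.** Inputs from Section 15.3: difference 0.5, SD 1, power 90%, 5% significance. Tests are one-sided (Section 16.1.1).

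- n per group = 2 × (1.645 + 1.282)² × 1² / 0.5² = 68.5, so 69. The t-based value is 69.2, which rounds up to the stated 70. A two-sided 5% test would need 85, so the stated figure is a one-sided one.
- Power with 70 against 70: Φ(0.5/√(2/70) − 1.645) = Φ(2.958 − 1.645) = 0.905.
- 4 × 70 = 280, and 280/0.8 = 350. Both reproduce.

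**2. What one low cohort does to pooled variance.** With four equal cohorts, a fraction p = 1/4 lower by d = 0.5, and within-cohort SD s:

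pooled variance R = s² + p(1 − p)d² = s² + 0.25 × 0.75 × 0.25 = s² + 0.047.

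With control SD 1, R is 1.047 at s = 1, 1.257 at s = 1.1 and 1.609 at s = 1.25.

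**3. How often the condition is met.** The protocol does not give the number of PROVENT controls for this comparison, so m = 70, 280 and 3,000 are assumed. For a one-sided 5% variance-ratio test:

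P(open) = P(F > c/R), where F has 279 and m − 1 degrees of freedom and c is its upper 5% point (1.393, 1.218 and 1.151 for the three values of m).

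| Within-cohort SD | Reading of the condition | Opens (m = 70 to 3,000) | Stays shut |
|---|---|---|---|
| 1.0 | significant, one-sided 5% | 8% to 13% (10% at m = 280) | 87% to 92% |
| 1.0 | numerically larger (c = 1) | 61% to 69% | 31% to 39% |
| 1.1 | significant, one-sided 5% | 31% to 84% | 16% to 69% |
| 1.25 | significant, one-sided 5% | 79% to nearly 100% | 0% to 21% |

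Direct simulation of the four-cohort mixture agrees to within about one percentage point. A two-sided 5% variance test at SD 1 stays shut more often, in 91 to 95% of trials (from 70 controls up to a known control variance).

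**4. Whether the pooled mean covers the gap.** One cohort 0.5 lower moves the pooled mean by 0.5/4 = 0.125. Power = Φ(0.125/√(1/280 + 1/m) − 1.645), which is 24% at m = 70, 43% at 280 and 64% at 3,460. The direct test of that cohort has 90.5% with only 70 controls.

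**5. Timing of the look.** Section 9.3 gives 3 to 6 months' accrual. With uniform accrual, the 280th day-28 dataset arrives 28 days (0.92 months) after the 280th patient who will supply one has enrolled.

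- 6 months, no loss by day 28: 350/6 = 58.3 per month; 280/58.3 + 0.92 = 5.72 months; 58.3 × 5.72 ≈ 334 enrolled, 16 places left.
- 6 months, 10% loss: 280/0.9 = 311; 311/58.3 + 0.92 = 6.25 months, so all 350 are enrolled.
- 3 months, no loss: 2.40 + 0.92 = 3.32 months, so all 350 are enrolled. The same holds at 4 months.

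**The case against.** Four counter-arguments have substance.

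**Cohort results appear anyway.** A reader might infer that a shut condition means no cohort-level result at all. The documents do not support that: Sections 6 and 16.1.1 provide cohort comparisons and summaries unconditionally. What is conditional is the progression to individual cohorts in Sections 15.3 and 16.1.2. The protocol therefore contradicts itself on this step, and the shut rates apply only to the conditional route.

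**The condition may be looser, or more easily met.** Section 15.3 asks for a significant difference or greater variability, and Section 16.1.2 only for a greater variance, so a purely numerical reading is open. Section 15.3 also expects patients to be more variable than healthy volunteers and gives this as the reason for sizing each cohort. Both points stand, and they rule out a miss rate of about nine in ten as a general figure. They do not rescue the rule. The expected excess is not quantified and the sizing uses SD 1. The numerical version opens about half the time when there is no difference at all. And where the condition opens readily, within-cohort spread opens it and not the mean deficit.

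**A uniform deficit is not missed.** If all four cohorts are 0.5 lower, pooled variance is unchanged and the significance condition opens in only 5% of trials, but the pooled mean comparison would detect the deficit. That is correct, so this scenario is not counted here.

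**Adaptation remains possible after the look.** A reader might conclude that the adaptation can never act. That goes too far: Section 15.3 allows targets to be re-estimated, Section 6 allows recruitment to be extended, and Section 16.2 exempts the adaptation analyses from its statement that no other subgroup analyses are planned. The narrower point remains that extension would exceed the cap of 350, and that closure comes too late to matter.

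**Conclusion.** The concern holds in a limited form. Sections 15.3 and 16.1.2 place a pooled variance condition in front of cohort mean comparisons that were each sized for 90% power, and Sections 6 and 16.1.1 describe cohort comparisons without it. The stated per-cohort power is not delivered whenever the condition fails.

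How often it fails depends on things the protocol leaves open: the reading of the condition, the number of controls, and the patients' within-cohort SD. At the planning SD, with one cohort 0.5 lower, the range runs from about 31% (numerical reading, most controls) to 92% (significance reading, fewest controls). With clearly larger patient variance the condition mostly opens. No single rate should be quoted.

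On timing, under uniform accrual over 3 to 6 months, about 334 to all 350 patients are enrolled when the 280th day-28 dataset is complete. Closing or rebalancing cohorts within 350 is then practically impossible.

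This should be corrected. The protocol itself fixes both the condition and the trigger, so it is not a detail to leave to the SAP.

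**What to change.** Delete the variance conditions in Sections 15.3 and 16.1.2, and align the similar sentence in Section 4.7. State that the mean difference from controls is estimated and tested in each of cohorts 1 to 4 unconditionally, consistent with Sections 6 and 16.1.1, with the pooled and variance comparisons reported as additional results.

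Since recruitment is paused, remove the expand-or-close statements in Section 6 and the matching adaptive wording in Sections 3.2 and 4.7, or say plainly that the adaptation cannot operate within 350. Describe the design as a fixed-sample comparison of four cohorts.

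The cost is wording only, with no change to data collection or patient numbers. The statistical price is that four cohort tests are always reported. If familywise control is wanted, Holm's first step is at one-sided 5%/4 = 1.25%, with power Φ(2.958 − 2.241) = 0.76 for a 0.5 deficit with 70 against 70.
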